
Over the course of the project, 334 adolescents provided consent to contact. Forty-one of these youth were not eligible, 9 declined participation, and 69 were not able to be contacted within the field period. Thus, 215 adolescents screened in as eligible to be in the project (see Fig. 1). Of these adolescents, 30 did not

complete their baseline assessment within the field period or hand unreliable contact information. This yielded a final enrolled sample of 185 adolescents who completed a baseline survey.

Measures

Demographics—Initially, adolescents had to either verbally self-identify as AI/AN or be identified as AI/AN by a parent or community member to participate in the project ([name] et al., 2019). In a subsequent self-report survey using categories established by NIH, participants checked “all that apply” for the following categories: AI/AN, Hispanic or Latino/Latina, Asian or Asian American, Native Hawaiian or Pacific Islander, black or African American, white or Caucasian, and other. Adolescents reported their age, gender, and level of education for each parent or guardian.

AOD use—We assessed substance use with the well-established Monitoring the Future items (Miech, Johnston, O’Malley, Bachman, & Schulenberg, 2016). Adolescents reported past 3-month use for cigarettes, alcohol, and marijuana. For this study, we created a dichotomous indicator of whether adolescents reported any use of these substances. This is because AOD use rates are typically lower in younger adolescents, leading to highly skewed distributions in continuous variables ([name] et al., 2016).

Consequences of alcohol and marijuana use—Adolescents reported on the consequences they had experienced in past three months. Consequences are based on DSM- IV criteria with 7 items for alcohol (e.g., missed school or work) and 5 for marijuana (e.g., had difficulty concentrating) ([name] et al., 2016). Both scales have been used extensively with adolescents and were reliable with teens in this study ($\alpha = 0.77$ for marijuana and $\alpha = 0.94$ for alcohol). For this analysis we created dichotomous indicators of whether adolescents reported any consequences from alcohol or any consequences from marijuana.

Intentions to use AOD—Three separate items assessed whether adolescents believed they would drink any alcohol, use any marijuana, or smoke a cigarette in the next six months (1=“definitely yes” to 4=“definitely no”) (Ellickson, McCaffrey, Ghosh-Dastidar, & Longshore, 2003).

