Resistance self-efficacy (RSE): ([name] et al., 2012) for alcohol was defined as the average of four items rated from “I would definitely use” to “I would definitely not use” based on different situations (e.g., if my best friend were using; you were bored at party; your friend gives you a drink). RSE ranged from 1 to 4; higher scores indicated greater RSE ($\alpha = 0.94$).

Peer influence—Three separate items assessed how often adolescents spend time around teens who drink, use marijuana, or smoke cigarettes (1 = “never” to 4 = “often”) ([name], Miles, Stern, & Meredith, 2008).

Intentions to participate in traditional practices—Adolescents reported how likely they were to participate in >20 different traditional practices (e.g., going to Pow Wows, prayer, playing Native hand or stick games) in the next six months (1=“definitely yes” to 4=“definitely no”). Items were based upon extensive research conducted with AI/AN adolescents, parents, and community partners ($\alpha = 0.97$) (Kaufman et al., 2014).

Cultural pride and belonging—We assessed adolescents’ AI/AN cultural pride and sense of belonging with the Multigroup Ethnic Identity Measure (MEIM), which has twelve items ($\alpha = 0.94$). Respondents are asked the degree to which they agree with statements such as, “I have a clear sense of my ethnic background and what it means to me” on a scale from 1 = “strongly disagree” to 5 = “strongly agree” (Phinney & Ong, 2007; Ponterotto, Gretchen, Utsey, Stracuzzi, & Saya, 2003). Given that our prior focus group work (Brown et al., 2016) indicated that many adolescents were of mixed ethnicity, and our focus was on AI/AN identity, we modified these items to focus on AI/AN heritage (e.g., “I have clear sense of my AI/AN identity and what it means to me”).

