of longitudinal linear and logistic regression models. The models included an indicator for being randomized to the intervention group and the following covariates: baseline value of the outcome and demographics (age, gender, and race/ethnicity [self-identification as Hispanic, multi-racial, or other vs. AI/AN]). Because follow-up surveys were administered over a somewhat wide timespan from the intended 3-month and 6-month time points (the interquartile range was 80–158 days for administration of the 3-month survey and 170–243 days for the 6-month survey), models additionally adjust for the number of days between the end of the treatment period and the follow-up survey date, as well as which follow-up survey the response is from. Because each adolescent contributed two records (3- and 6-month follow up) to this analysis, standard errors were adjusted for clustering on individuals with SAS Proc SURVEYREG and SURVEYLOGISTIC. Among the intervention group only, a similar set of regressions was fit to estimate the effect of each intervention session.

Missing data

All analyses of responses to follow-up surveys were based on imputed data. SAS Proc MI was used to generate 40 imputed datasets for all variables used in the analysis at all time points, including for completely missing follow-up surveys. Imputed values were truncated to their original minima and maxima. SAS Proc MIANALYZE was used post-analysis to compile results across the 40 imputed datasets.

Descriptive statistics

Means at follow-up were calculated as the mean of the means from each of the 40 imputed data sets. Standard deviations were calculated using standard rules for multiple imputation (Rubin, 2004), which estimates the overall variance as the average within-imputation variance plus the product of the between-imputation variance and $1 + (1/m)$ where m = the number of imputations (40).

Loss to follow-up

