Rates of use for the overall sample remained fairly stable over time, with 23% of the sample reporting alcohol use in the past 3 months at baseline, and 30% of the sample reporting use at 6 months. Similarly, for marijuana, 28% of the sample reported use in the past three months at baseline, and 29% reported use in the past three months at the six month follow up. Intentions to drink and use marijuana were also stable for the overall sample over the course of the study, as was the time that teens spent with peers who used alcohol, tobacco, and marijuana. Of note, tobacco use for the overall sample appeared to increase over time, as did the number of teens reporting consequences from drinking or marijuana. Among those who were randomized to the MICUNAY + CWG group, 21 (18%) attended no workshops, 17 (15%) attended one workshop, 11 (10%) attended two workshops, and 66 (57%) attended all three MICUNAY workshops. The effect of each additional session of MICUNAY attended in this group was small, with an estimated effect size of about 0.15 or less in magnitude for each outcome. Three outcomes had moderately sized associations and marginal p- values: intentions to drink alcohol, alcohol resistance self- efficacy, and intentions to participate in cultural activities. For example, for each MICUNAY session attended, the average alcohol resistance self-efficacy response was estimated to be 0.19 higher, with an effect size of 0.17 and a p-value of 0.04. However, the confidence interval for this effect is large, and after adjusting for performing tests on all 16 outcomes, the Bonferroni-adjusted p-value was 0.64. Although the Bonferroni adjustment is likely conservative, we conclude that there is not strong evidence in favor of a treatment effect for MICUNAY + CWG on these outcomes.

Primary outcomes

- a) Alcohol Use -- this is a Standard Question Used in Monitoring the Future. [Time Frame: change from baseline to 6 months]
- b) Marijuana Use--this is a Standard Question Used in Monitoring the Future. [Time Frame: change from baseline to 6 months]

Secondary outcomes

- a) Consequences of Alcohol Use - [Time Frame: change from baseline to 6 months]
- b) Consequences of Marijuana Use - [Time Frame: change from baseline to 6 months]
- c) Intentions to Use - Alcohol [Time Frame: change from baseline to 6 months]
- d) Intentions to Use - Cigarettes [Time Frame: change from baseline to 6 months]

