- e) Intentions to Use - Marijuana [Time Frame: change from baseline to 6 months]
- f) Alcohol Resistance Self-efficacy [Time Frame: change from baseline to 6 months]
- g) Peer Influence - Alcohol [Time Frame: change from baseline to 6 months]
- h) Peer Influence - Marijuana [Time Frame: change from baseline to 6 months]
- i) Peer Influence - Cigarettes [Time Frame: change from baseline to 6 months]
- j) Intentions to Participate in Traditional Practices [Time Frame: change from baseline to 6 months]
- k) Cultural Identification [Time Frame: change from baseline to 6 months]
- l) Spirituality/Happiness [Time Frame: change from baseline to 6 months]

Risk factors

Unique risk factors may predispose urban AIs/ANs to initiate AOD use during adolescence. For example, experiences of acculturative stress directly and indirectly associated with historical trauma experienced by AIs/ANs throughout U.S. history have been shown to result in poor mental health outcomes. Among urban AI/AN youth, acculturative stress may also play a role in AOD use as identity issues among urban AI/AN adolescents have been postulated to contribute to lower self-worth, which is associated with the genesis and maintenance of AOD problems. In addition, a variety of psychosocial and environmental risk factors, such as witnessing domestic violence, physical/sexual/emotional abuse, issues associated with stigma, and family histories of mental health and substance abuse may increase AOD use among urban AI/AN youth. Thus, these stressors may increase the potential for AOD use due to issues associated with cultural identity, decreased spiritual base, and lack of community cohesion. Providing an AOD program that incorporates traditional healing activities, promotes community involvement, and encourages healthy notions of AI/AN identity may increase wellbeing and other healthy behaviors by addressing sources of stress linked to cultural identity, stigma, and community connections. However, few evidenced-based programs have been successfully developed and implemented among urban AI/AN youth that integrate such important cultural elements.

Surveys and scales

All youth will complete surveys at baseline, 3- and 6-months that will focus on behaviors of AI/AN

participants as they relate to AOD use.

Scale names

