For the secondary measures, “Intentions to Participate in Traditional Practices” and “Cultural Identification,” we used the Multigroup Ethnic Identity Measure (MEIM), which has twelve items ($\alpha = 0.94$). Respondents are asked the degree to which they agree with statements such as, “I have a clear sense of my ethnic background and what it means to me” on a scale from 1 = “strongly disagree” to 5 = “strongly agree”. Given that our prior focus group work indicated that many adolescents were of mixed ethnicity, and our focus was on AI/AN identity, we modified these items to focus on AI/AN heritage (e.g., “I have clear sense of my AI/AN identity and what it means to me”).

For the secondary measure, “Spirituality/Happiness,” we used a subset of ten items from the 12-item Functional Assessment of Chronic Illness Therapy-Fatigue-Spiritual Questions instrument, or FACIT-SP 12. Adolescents reported agreement with statements such as “I find comfort in my faith or spiritual beliefs” and “I feel a sense of harmony within myself.” Two items that referred specifically to chronic illness were removed from the scale as they were not relevant for this study. Response options, which ranged from 1=“not at all” to 5=“very much,” were averaged ($\alpha = 0.83$), with negative statements reversed such that higher scores indicated greater spirituality and happiness.

Safety outcomes

Adverse event reporting policy

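### SAP Scale names gives secondary outcomes j and k the same instrument, and the printed coding of the substance-use intention items runs opposite to the reading of the reported means

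*Combined protocol and SAP*

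**What the plan says.** **Instruments.** Protocol, Measures, describes two separate tools. For traditional-practice intentions, "Adolescents reported how likely they were to participate in >20 different traditional practices" over the following six months, from 1 at the yes end to 4 at the no end (alpha 0.97). For cultural identity it assessed "cultural pride and sense of belonging with the Multigroup Ethnic Identity Measure (MEIM), which has twelve items", answered from 1 to 5 with 5 the strongest agreement (alpha 0.94). SAP, Scale names, says: "For the secondary measures, “Intentions to Participate in Traditional Practices” and “Cultural Identification,” we used the Multigroup Ethnic Identity Measure (MEIM"). It goes on to give the MEIM's item count, response scale and alpha, and does not mention the practice list. SAP, Secondary outcomes, lists two entries: "j) Intentions to Participate in Traditional Practices [Time Frame: change from baseline to 6 months" and "k) Cultural Identification [Time Frame: change from baseline to 6 months". In SAP, Outcomes, the session analysis names three outcomes with marginal p-values, the last being "and intentions to participate in cultural activities".

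**Coding.** Measures has three separate intention items, for alcohol, marijuana and cigarettes (outcomes c, e and d). The anchors are printed as "smoke a cigarette in the next six months (1=“definitely yes” to 4=“definitely no"), and no reversal is stated. SAP, Baseline differences and attrition, says that youths with at least one follow-up survey had lower marijuana intentions than those with none, with means of 1.67 and 2.29 (p = 0.01). For resistance self-efficacy and for spirituality/happiness the document does say that a higher score means more of the construct.

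**The concern.** The section whose job is to name the scales gives outcome j an instrument that does not ask about intentions and that contradicts Measures. Anyone scoring j from that section would compute the same number for j and k, although they are listed as two outcomes.

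The second conflict concerns sign. With yes at 1, a lower mean is a stronger intention, yet the attrition text reads it as a weaker one. A person scoring from Measures would get the opposite direction to the reported text. This matters for reading results because intention to drink (c) and, apparently, j are two of the three outcomes singled out in the session analysis, and no signed estimate is printed for either.

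**Working it through.** **1. Instrument for outcome j.** No arithmetic applies, so the descriptions are set side by side.

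| | Measures, for j | MEIM: in Measures for cultural pride and belonging; in Scale names for both j and k |
|---|---|---|
| Items | more than 20 | 12 |
| Range | 1 to 4 | 1 to 5 |
| Printed direction | 1 = yes end | 5 = strongest agreement |
| Alpha | 0.97 | 0.94 |
| Content | likelihood of taking part in practices | sense of AI/AN identity |

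They differ on every row, so these are not two descriptions of one tool. Taken literally, Scale names leaves 12 − 1 = 11 distinct secondary scores, or 13 of the 2 + 12 = 14 listed outcomes.

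**2. Direction of the marijuana-intention item (outcome e).**

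Inputs: means 1.67 and 2.29, p = 0.01, and 89% of 185 with a follow-up (Baseline differences and attrition); 28% past-3-month marijuana use at baseline (same section, and Outcomes); a 1–4 item (Measures). Assumption: points 1 and 2 form one half of the item and 3 and 4 the other, since the middle labels are not printed.

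- *Group sizes.* 164 and 21 reproduce the printed percentages: 164/185 = 88.6%; among those without follow-up, tobacco use 9/21 = 42.9% (printed 43%) and heavy drinking 6/21 = 28.6% (printed 29%).
- *Pooled mean.* (164 × 1.67 + 21 × 2.29)/185 = (273.88 + 48.09)/185 = 1.740.
- *Bound.* For mean m on a 1–4 item, the share on points 3–4 is largest when those youths all answer 3 and everyone else answers 1. That share is (m − 1)/2, so at least 1 − (m − 1)/2 are on points 1–2.
- *Printed coding (1–2 = yes half).* With follow-up: 1 − 0.67/2 = 66.5%. Without: 1 − 1.29/2 = 35.5%. Pooled: 1 − 0.740/2 = 63.0%. Taking the no-follow-up share anywhere from 8% to 15% gives 64.0% to 61.9%, so the exact split hardly matters.
- *Reversed coding (3–4 = yes half).* Pooled: at most 0.740/2 = 37.0%.
- *Comparison.* 28% reported recent use. That sits easily with at most 37% intending use, and much less easily with at least 63%.
- *What the printed anchors would show.* If the same answers were expressed on the printed coding, the reported lower intention would appear as 5 − 1.67 = 3.33 against 5 − 2.29 = 2.71.
- *Are these credible item means?* SDs are not printed, so p = 0.01 cannot be reproduced directly. Working back, SD = 0.62/(2.603 × √(1/164 + 1/21)) = 0.62/(2.603 × 0.2318) = 1.03, which is plausible for a 1–4 item. The conflict is about direction, not about an impossible mean.

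The surrounding text points the same way. Those with follow-up had less tobacco use (12% vs 43%), less heavy drinking (11% vs 29%) and less time with teens who smoke (1.53 vs 2.14, where the printed anchors do make lower mean less). Lower marijuana intention fits that profile; higher intention would not.

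**The case against.** The strongest reply is that both conflicts nearly resolve themselves. Measures gives the practice list its own alpha, and Scale names simply repeats the MEIM description, none of which concerns intentions. The Outcomes section counts 16 outcomes; the 14 listed plus tobacco use and heavy drinking make 16 only if j and k are separate. That tally is an inference, because the 16 are not itemised, but it supports a labelling slip. The wording of the session result also matches the practice list. On direction, the attrition text itself shows how e was read. The bound compares intention over the next six months with use over the past three, so it supports reversal without proving it. All of this stands. It limits the point to an error of consistency, but it does not make the two texts agree.

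A reader might infer more, and the documents do not support it:

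- *That j was actually analysed with the MEIM, so its marginal session result is wrong.* Only the mislabelled sentence suggests this. The size of any change cannot be estimated either, because the correlation between the two scales is not printed and even its sign depends on how j was coded.
- *That the wrong label distorts the imputation.* The rule is "Imputed values were truncated to their original minima and maxima", which refers to the variable analysed, whatever it is called.
- *That intention effects are reported with the wrong sign, or that the attrition statement is wrong.* No signed treatment or session estimate is printed for c, d, e or j, and an unstated reversal would leave the attrition statement correct.
- *That benefit for j is undefined.* The SAP describes taking part in traditional practices as protective, so the desired direction is clear. Only the numeric coding is unstated, and no printed mean for j contradicts its anchors.

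**Conclusion.** The point holds as a minor consistency error confined to secondary outcomes. One of the 12 (j) carries an instrument in Scale names that contradicts Measures, most likely through a labelling slip. One of the 12 (e) has printed anchors that run against the reading of its means, most likely because of an undocumented reversal or misprinted anchors. Outcomes c and d come from the same item block and probably share the problem. Outcome j has anchors of the same form, so its coding should be confirmed as well.

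The case for reversal rests on whole-number answers from 1 to 4, on the 1–2 against 3–4 split, and on comparing different time windows. No primary outcome, printed treatment estimate or overall conclusion is shown to change.

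**What to change.** - Check the scoring code for c, d, e, j and k first.
- Correct Scale names so that j carries the list of more than 20 practices, with its scoring rule, and the MEIM is named for k only.
- State the coding analysed for c, d, e and j, so that signs can be read. Then either correct the anchors in Measures or state the reversal, to match the code. If the code shows no reversal for e, it is the attrition sentence that needs correcting.
- Re-run j with the practice list only if the code shows that it was scored with the MEIM, and report the new effect size and p-value.

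The cost is a check of the code and a few lines of text. No new data are needed, and no re-analysis unless the last case applies.
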